## **5.3. Recruitment**

### **5.3.1. Sample identification**

All attendees of the Greater Manchester LHC service or MFT-CURE service who currently smoke are reviewed by a smoking cessation practitioner as part of the CURE team. At their clinical appointment, individuals who wish to stop smoking will be informed of the study by their clinical care team and if interested in taking part in research, will then be directed to discuss the study with a member of the research team who will be based on site. This will either be at the same visit or at another time depending on the preference of the individual.

### **5.3.2. Screening**

Patients will be screened by a member of the research team, prior to consent, to ensure that they are eligible for the study. This will be done via an eligibility check of the inclusion and exclusion criteria. An eligibility screening proforma will be used for this purpose. This document will collect data such as name, date of birth and whether the patient meets the inclusion criteria. It will be stored in the site file and serve as source document should there be any questions around eligibility to participate. This will be explained verbally to the patient by a member of the research team.

### **5.3.3. Consent**

A written participant information sheet (PIS) will be provided. This will give information about the purpose of the study, what participation entails and will highlight the benefits and risks of participation. It will be clearly stated that taking part is voluntary and whether they participate or not this will not impact the medical care they receive. The study will also be explained verbally by a member of the research team. Participants will be given adequate time to review the information and have the opportunity to ask any questions they may have about the study.

Fully informed written consent is required prior to participation in the study. This will take place on the day of the study visit and will involve the participant signing a paper consent form. Consent will be taken by an appropriately trained member of the research team, who will also sign the consent form and give the participant a copy to take home. Participants are free to withdraw from the study at any time, without needing to give a reason. If a participant would like to leave the study the research team will ask for all data and samples collected up to the time of withdrawal to be kept; however, participants have the right to have data removed from the research database and samples collected as part of the study destroyed.

## **5.4. Biological sample collection**

All samples will be collected at the time of the study visit, following Standard Operating Procedures. Buccal swabs, nasal swabs, nasal brushes and blood samples will be collected by a suitably trained member of the research team. The mouthwash sample will be collected by the participant, under the guidance of a member of the research team. The breath carbon monoxide measurement will be performed by the clinical care team or a member of the research team.

## PROMINENT Smoking Cessation Study

**5.4.1. Timepoint 1 (TP1)**

Samples collected at baseline include the following

- Buccal swab
- Mouthwash sample
- Breath carbon monoxide measurement
- Personal data collection form
- Study questionnaire
- Nasal swab (optional)
- Nasal brush (optional)
- Blood sample (optional) – 50mL volume maximum

If it is not possible to take the nasal sample (brush or swab) for whatever reason the individual may continue in the study. If the buccal sample is not collected, then the individual will be withdrawn from the study.

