## 2. RESEARCH QUESTION/ AIM(S)

**Main research question:** What is the impact of smoking cessation on the molecular characteristics on nasal and buccal cells, and does exposure to e-cigarettes lead to specific molecular changes in these tissues?

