### 2.1. Objectives

#### 2.1.1. Primary

- Understand how smoking cessation affects normal nasal and buccal cells to modify tumorigenesis risk.
- Understand how e-cigarettes affects normal nasal and buccal cells compared to individuals who continue to smoke and individuals who have stopped smoking without the use of e-cigarettes.

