### 5.2. Sampling

#### 5.2.1. Size of sample

The study is exploratory; the primary aim is to analyse paired sequential samples from current smokers who successfully quit smoking. Based on our data, approximately 20% of current smokers are able to quit therefore to ensure a minimum of 50 paired samples, up to 250 current smokers will be recruited at baseline. We also aim to recruit paired samples from participants who are current smokers at baseline and at timepoint 3.

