## 9. APPENDICES

### 9.1. Appendix 1 – Schedule of Procedures

Procedures	Visits		
	Visit 1 (TP1 Baseline)	Visit 2 (TP3 Follow-up)	Visit 3 (TP4 Follow-up)
Screening	X		
Informed consent	X		
Personal data collection form	X		
Study questionnaire	X	X	X
Buccal cell collection	X	X	X
Nasal swab collection (optional)	X	X	X
Nasal swab collection (optional)	X	X	X
Blood sample (optional)	X	X	X
Mouthwash collection	X	X	X
Carbon monoxide measurement	X	X	X

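### Section 5.2.1 gives 50 quit pairs as a minimum, but 50 is only the no-loss expectation at 250 recruits, and optional nasal sampling makes the expected nasal number smaller

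*Protocol*

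**What the plan says.** The main research question (Protocol section 2) asks "What is the impact of smoking cessation on the molecular characteristics on nasal and buccal cells". The first primary objective (2.1.1) is "Understand how smoking cessation affects normal nasal and buccal cells to modify tumorigenesis risk", and the second is "Understand how e-cigarettes affects normal nasal and buccal cells compared to individuals who continue to smoke" and to people who stopped without e-cigarettes. All three name the two tissues side by side, with no ranking.

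The collection rules do rank them. Sections 5.4.1, 5.4.3 and 5.4.4 mark both the nasal swab and the nasal brush as optional at TP1, TP3 and TP4, and Appendix 1 marks nasal collection as optional too. Under TP1, section 5.4.1 states: "If it is not possible to take the nasal sample (brush or swab) for whatever reason the individual may continue in the study". The next sentence withdraws anyone without a buccal sample.

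Section 5.2.1 describes the study as exploratory and ties its primary aim to paired samples from people who quit. Its sizing rests on one input, that "approximately 20% of current smokers are able to quit", and concludes: "to ensure a minimum of 50 paired samples, up to 250 current smokers will be recruited at baseline". It names no tissue and includes no term for missed TP3 visits or for nasal uptake.

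Appendix 1 has two identical rows reading "Nasal swab collection (optional)" and no row for the nasal brush.

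**The concern.** A reader of section 5.2.1 takes 50 as the smallest number of quit pairs the primary analysis will have. The number is attached to the primary aim, and nasal cells are one of only two tissues in that aim, so the natural reading is that it covers both. Yet the design requires only the buccal sample, and the calculation already uses the whole recruitment cap.

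What is at stake is how the results are read. If nasal findings rest on fewer people than buccal findings, and the plan has said nothing to prepare for it, a weak nasal result may be taken for a biological difference between tissues when it partly reflects a smaller number of pairs. People who give nasal samples twice may also differ from those who do not, although the documents give no information on this.

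**Working it through.** **Inputs from the Protocol.** Cap on recruitment: 250 (5.2.1). Quit rate: 20% (5.2.1). Planned range: 150 to 250 (Study Summary). A pilot of the CURE project gave a self-reported 12-week quit rate of 22% (1.2). No TP3 attendance rate and no nasal uptake rate are given.

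**Step 1: reproduce the stated figure.** Recruits needed = pairs / quit rate = 50 / 0.20 = 250. Equivalently, 250 x 0.20 = 50. This matches exactly, and only if every quitter attends TP3 and gives usable samples at both visits.

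**Step 2: is 50 a minimum?** With 250 recruits each quitting with probability 0.20 and no losses, the binomial chance of at least 50 quitters is 0.53. At a 22% quit rate, 250 x 0.22 = 55 are expected and the chance is 0.80. With 10% or 20% of quitters lost before TP3 (assumed), expected buccal pairs are 50 x 0.9 = 45 or 50 x 0.8 = 40. At the lower end of the planned range, 150 x 0.20 = 30.

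**Step 3: nasal pairs.** Let u be the share of quitters with nasal samples at both TP1 and TP3. Before attrition:

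- expected nasal pairs = 250 x 0.20 x u = 50u
- recruits needed for 50 expected nasal pairs = 50 / (0.20 x u)
- chance of at least 50 nasal pairs = binomial upper tail with n = 250 and probability 0.20 x u

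| u (assumed) | Expected nasal pairs at 250 | Recruits needed for 50 | Chance of at least 50 |
|---|---|---|---|
| 90% | 45 | 278 | 0.23 |
| 80% | 40 | 313 | 0.05 |
| 70% | 35 | 358 | 0.006 |
| 60% | 30 | 417 | below 0.001 |
| 50% | 25 | 500 | below 0.001 |

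Every figure in the third column exceeds the cap of 250.

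**Step 4: how u relates to uptake at each visit.** If uptake at each visit is p and the same people accept both times, u = p. If acceptance is independent between visits, u = p x p, so p = 80% gives 50 x 0.64 = 32 pairs. Someone who accepted once is likelier to accept again, so the independent case is best read as a pessimistic bound.

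**Step 5: both losses together.** With 10% lost before TP3 and u = 80% among those who attend, expected nasal pairs are 50 x 0.9 x 0.8 = 36.

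**The case against.** The strongest reply is that the protocol never promises 50 nasal pairs. Section 5.2.1 names no tissue, the study is exploratory, and no power, error rate or effect size depends on reaching 50. Making an uncomfortable sample optional is a reasonable and visible choice; section 6.7 itself mentions irritation from the brush. Most of this stands, and nothing here asks for nasal sampling to be compulsory. It does not rescue the sentence in 5.2.1, which claims to secure a minimum for the primary aim when nasal cells are half of that aim and the arithmetic has no slack.

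It is also fair to say that the size of the shortfall is assumed. Uptake appears nowhere in the protocol, so only the direction is established. The main comparison is within person, baseline against TP3 (3.3), which limits bias from stable differences between nasal donors and others.

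Four stronger readings may tempt a reader, and the documents do not support them:

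- *The 50 is sound for buccal cells and fails only for nasal cells.* Step 2 shows that it is not secured for buccal cells either.
- *Nasal pairs will be split between swab and brush, so a same-device rule is needed.* Sections 5.4.1, 5.4.3 and 5.4.4 list both devices at each sampling visit. The mention of brush or swab in 5.4.1 only describes what happens when a nasal sample is missing.
- *Staff following Appendix 1 would collect no brush.* This is a single-centre study with trained staff, and the brush is named throughout section 5.4. The repeated row looks clerical.
- *Nasal cells must be removed from the primary objectives.* That is a debatable trade-off. Section 1 gives nasal mucosa its own rationale as a stand-in for bronchial epithelium, and an honest count can sit beside an unchanged objective.

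**Conclusion.** The point holds as a misstatement of size in section 5.2.1. At the stated inputs, 50 is the mean number of quit pairs at full recruitment with complete follow-up, and it is reached or exceeded with probability of about one half. For nasal cells the expected number is below 50 at any uptake under 100%, and no recruitment within the cap restores it at a 20% quit rate.

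The direction rests only on the protocol's own figures and on the optional status of the nasal samples. The size rests on an assumed u. The probabilities also assume that participants quit independently at a common rate and that, beyond u, nothing is lost before TP3. A quit rate above 20% would ease the shortfall: at 22% and u = 90%, 55 x 0.9 = 49.5 nasal pairs are expected. Lower attendance or fewer than 250 recruits would worsen it.

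The study's validity is not in question. What needs correcting is a number that readers will use to judge how much weight each tissue's result can bear.

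**What to change.** 1. In section 5.2.1, replace the claim of a minimum. State that 50 is the expected number of buccal quit pairs at 250 recruits and a 20% quit rate, before attrition.
2. In the same section, add a separate and smaller expected number of nasal pairs, calculated from the share of participants who have given nasal samples so far, and state that share.
3. State that nasal results will be reported with their own number of pairs, as a subset defined by optional sampling.
4. As a minor editorial correction, change the second of the two identical nasal swab rows in Appendix 1 to the nasal brush, to agree with section 5.4.

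The cost is a change of protocol wording plus a count from existing sampling records. It needs no extra participants, visits or samples. The change goes through the amendment route in section 6.3, where the Chief Investigator decides with the sponsor whether it is substantial. The price is that the stated nasal number becomes visibly smaller. The primary objectives can stay as they are, and no rule on matching nasal devices between visits is required.

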**5.4.2. Timepoint 2 (TP2)**

Study participants will be contacted by a member of the research team to ascertain smoking status. This will be undertaken over the telephone and will involve the completion of a study questionnaire. It is anticipated that phone calls will be made every 3 months to ascertain smoking status. TP3 will be arranged if the participant has not smoked a cigarette for at least three consecutive months prior to the proposed date of TP3. If by 3-12 months after baseline a participant remains a current smoker (smoked within three months of the telephone assessment) they will then have TP3 arranged.

**5.4.3. Timepoint 3 (TP3)**

Samples collected at TP3 include the following

- Buccal swab
- Mouthwash sample
- Breath carbon monoxide measurement
- Study questionnaire
- Nasal swab (optional)
- Nasal brush (optional)
- Blood sample (optional) - 50mL volume maximum

TP3 participants will be classified as either **a former smoker** (last cigarette over three months ago i.e. a last cigarette 3 months plus 1 day ago = former smoker) **or current smoker** (smoked a cigarette within the last three months).

## PROMINENT Smoking Cessation Study

**5.4.4. Timepoint 4 (TP4)**

Participants who attend TP3 who are classified as a former smoker will be invited to attend a further appointment 3 to 6 months after TP3 (TP4). Samples collected at TP4 include the following

- Buccal swab
- Mouthwash sample
- Breath carbon monoxide measurement
- Nasal swab (optional)
- Nasal brush (optional)
- Blood sample (optional) – 50mL volume maximum

Study questionnaires will be completed by the participant, at all timepoints, either at the study visit or over the telephone (with a member of the research team recording the participant's response to questions). This can be completed electronically (an electronic device will be available on site for this purpose) or on paper.

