**STUDY SUMMARY**

Study Title	Discovering the molecular signatures of cancer PROMotion to INform prevention (PROMINENT): Smoking Cessation Study
Internal ref. no. (or short title)	PROMINENT: Smoking Cessation Study (Sponsor Reference Number: NHS002126)
Study Design	Observational study
Study Participants	Current smokers, aged ≥55 years old, no prior history of cancer
Planned Size of Sample (if applicable)	150 - 250
Follow up duration (if applicable)	Between 3 and 12 months after recruitment
Planned Study Period	3rd June 2024 – 31 st May 2027
Research Question/Aim(s)	Study the impact of smoking cessation on the molecular architecture of human buccal and nasal cells.

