#### 3.3. Data analysis

The clinical cohort will be stratified according to smoking status at timepoint 3 into a Quit Cohort (stopped smoking for 3 months or more at the time of sample collection) and a Smoking Cohort (smoked within 3 months of sample collection). Analysis of laboratory data will be stratified over time (baseline compared to timepoint three) and according to final cohort categorisation.

Machine learning algorithms will be developed to integrate across all of the features of the multi-omics analysis of normal tissues, to identify the combinations of parameters that contribute most to cancer risk. We will integrate salient features of the dynamics of tissue perturbation by tumour promoters including the clonal structure of tissues, protein and gene expression patterns, and differences in the pattern of infiltration of immune cell populations. In order to understand the association between these features and carcinogenesis. We will study whether they can be used to discriminate between groups of samples before or after intervention. We propose an analysis that is organized in logical steps with increasing degrees of complexity.

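### Section 3.3 pools all quitters at TP3 into one binary cohort and gives TP4 no role, so time since quitting is unused in the cessation and e-cigarette comparisons

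*Protocol*

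**What the plan says.** **Analysis.** Section 3.3 states: "Analysis of laboratory data will be stratified over time (baseline compared to timepoint three) and according to final cohort categorisation". The Quit Cohort is everyone who has stopped for three months or more at sampling. The section does not mention TP4 or time since the last cigarette.

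**TP3.** Under section 5.4.2, a quitter's TP3 is arranged once the person "has not smoked a cigarette for at least three consecutive months prior to the proposed date of TP3". Telephone calls are anticipated every three months. Section 5.4.3 makes the class binary: "last cigarette over three months ago i.e. a last cigarette 3 months plus 1 day ago = former smoker". For continuing smokers the rule is "If by 3-12 months after baseline a participant remains a current smoker". The quitter rule has no matching upper limit, but the Study Summary gives follow-up as "Between 3 and 12 months after recruitment".

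**TP4.** Under section 5.4.4, those classed as former smokers at TP3 are invited to "attend a further appointment 3 to 6 months after TP3 (TP4"). TP4 is thus timed from TP3 and not from the quit date.

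**E-cigarette objective.** Section 2.1.1 compares e-cigarette users with continuing smokers and with "individuals who have stopped smoking without the use of e-cigarettes".

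**The concern.** The background in section 1 describes recovery of tissue after quitting, including replenishment of the bronchial epithelium, and such a process takes time. A contrast that treats every quitter at TP3 as equally exposed to cessation averages over whatever mix of durations the visits happened to produce. It gives one number and no time course, although the study collects a second post-quit sample that would inform one.

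The second primary objective is more exposed. E-cigarette use is not randomised. If people who quit with e-cigarettes have been off cigarettes for less time at sampling than other quitters, or for more, part of the ordinary effect of abstinence time would be reported as an e-cigarette effect.

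**Working it through.** **1. The plan's own figure.** Section 5.2.1 expects 20% of up to 250 recruits to quit: 250 × 0.20 = 50 pairs. This reproduces, as an expected number. An even split by e-cigarette use, assumed here, gives 25 v 25.

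**2. Abstinence permitted at each visit.**
- TP3 floor: 3 months (5.4.2, 5.4.3).
- TP3 ceiling, calls acted on promptly: someone who reaches 3 months just after one call is found at the next, 3 months later, so TP3 falls at 3 to 3 + 3 = 6 months.
- TP3 ceiling, only the follow-up window binding: 12 months. It is about 12.5 if the last cigarette was up to 2 weeks before baseline, which section 5.1.2 allows.
- TP4 = TP3 + 3 to 6 months. Prompt calls: 3 + 3 = 6 to 6 + 6 = 12 months. Window only: 6 to 12 + 6 = 18 months.

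The quit group at TP3 therefore spans a twofold range of abstinence if the calls work and about fourfold if they do not.

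**3. Effect on the e-cigarette comparison.** The protocol gives no reversal curve, effect size or SD, so these are assumptions. Let the share reversed after t months be f(t) = 1 − 2^(−t/h), with half-life h. At h = 6, f(3) = 0.29, f(6) = 0.50 and f(12) = 0.75. Suppose e-cigarettes have no effect of their own, the mean abstinence times are a (e-cigarette quitters) and b (other quitters), and the other quitters' cessation effect is 0.8 SD.

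Spurious gap = 0.8 × [f(b) − f(a)] / f(b). Standard error = √(2/25) = 0.283 SD. False-positive rate = Φ(gap/SE − 1.96) + Φ(−gap/SE − 1.96).

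| a v b (months), h = 6 | f(a), f(b) | Gap as share of f(b) | Gap (SD) | Gap/SE | False-positive rate |
|---|---|---|---|---|---|
| equal | – | 0 | 0 | 0 | 5% |
| 5 v 6 | 0.439, 0.500 | 12% | 0.098 | 0.35 | 6.4% |
| 4 v 5 | 0.370, 0.439 | 16% | 0.125 | 0.44 | 7.3% |
| 4 v 7 | 0.370, 0.555 | 33% | 0.266 | 0.94 | 15.6% |

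For 4 v 7 months the share is 25% at h = 3 and 38% at h = 12. Over h of 3 to 12 and effects of 0.5 to 1.0 SD, the false-positive rate runs from 7% to 27%. A mean of 7 months cannot arise if every TP3 falls at 3-6 months, so this row needs calls to be missed or visits delayed.

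**4. Effect on the plain TP1-TP3 test.** Relative to weighting each quitter by the reversal expected at their own duration, the unweighted mean test has efficiency mean(f)/√mean(f²). For t uniform on 3-12 months this is 0.988, 0.974 and 0.962 at h = 3, 6 and 12, a loss of about 1-4%.

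**5. Ordering of visits.** In a person who stays abstinent, TP4 is always 3-6 months later than TP3. Between people, with the TP3-TP4 gap uniform on 3-6 months, the chance that one person's TP3 is later in abstinence than another's TP4 is 0.0% if TP3 is uniform on 3-6 months, 0.9% on 3-7.5, 4.2% on 3-9 and 13.0% on 3-12.

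**The case against.** **Much of this is SAP content.** Covariates and model form are commonly left to an SAP, none is shown, and section 5.2.1 calls the study exploratory. That stands in part: section 3.3 excludes no covariate. But it does fix the laboratory contrast as baseline against TP3 by a binary cohort, and an SAP that followed it literally would leave time since quitting and the TP4 samples out.

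**The calls limit the spread.** If they work, TP3 is at 3-6 months and TP4 at 6-12, and the ranges do not overlap. This stands. The larger figures depend on calls or visits running late.

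**Stronger readings.** A reader might infer that timing TP4 from TP3 contaminates the stated contrasts. It does not, because TP4 enters none of them; any mixing comes from the TP3 spread. A reader might also infer that visit labels fail to order abstinence. Within a continuously abstinent person they do order it, so the paired comparison is sound; between people the order fails only if TP3 runs late. Nor do the documents show that the e-cigarette comparison is biased. The same call rule applies to all participants, and nothing indicates that abstinence time differs by e-cigarette use.

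**The data may not be there.** Section 3.2 records quit-attempt information at TP2 and TP3. No section gives the content of the TP4 questionnaire, and classifying someone at TP3 needs only an answer of over or under three months. This also stands, and the fix allows for it.

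**Conclusion.** The point holds as a cheap improvement to the analysis and not as an error that invalidates the TP1-TP3 contrast. Section 3.3 uses one binary quit group although abstinence at TP3 may range over about 3-6 months, or up to about 12, and it leaves the TP4 samples without a role. As written, it cannot describe how change depends on time since quitting.

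For the plain cessation test the cost is small, at 1-4%. For the e-cigarette comparison the risk is conditional. With equal abstinence times there is no bias. With a 1-month difference the false-positive rate is about 6-7%, and with 4 v 7 months it is 16%. Those rates assume a 6-month half-life, 25 v 25 quitters and a 0.8 SD effect, none of which the protocol states.

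**What to change.** In section 3.3:

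1. Keep the TP1-TP3 contrast by cohort.
2. Add a model of quitters' change from TP1 that uses the TP3 and TP4 samples together, with months since last cigarette as the time variable (log months or another 1-2 degree-of-freedom term) and person as a random effect.
3. In the comparison of people who quit with and without e-cigarettes, include months since last cigarette as a covariate.
4. Confirm that the TP3 and TP4 questionnaires record the date of last cigarette, and add the item if they do not.

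The cost is 1-2 degrees of freedom and possibly one questionnaire item. No visit, sample or eligibility rule changes. One limit remains: only former smokers are invited to TP4, so the later part of the fitted curve has no continuing-smoker samples beside it and should be reported as change within quitters.
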